**Table 5 – Missing Data Approaches**

Analysis	No FVC result but alive at Week 52	
	Handling of missing FVC result	Underlying assumption
Primary Estimand Analysis	Missing data handled by model.	Assumes missing at random. Discontinued subjects would have behaved similarly to subjects who did not discontinue who are in the same treatment group.
Sensitivity analysis	Based on the slope estimates for GB0139 dose and placebo among subjects who experience ICE without missing FVC data.	Subjects with a missing result would have behaved similarly to discontinued subjects with a result who are in the same treatment group.

The slope (SE) estimates of both treatment groups will be used in the sensitivity analysis. This approach is considered appropriate since the reasons for trial drug termination are expected to be similar between subjects with and without missing FVC data (discontinuation mainly due to AEs). The Sensitivity analysis corresponds to the assumption that in subjects with missing FVC data, the treatment effect would have persisted in the same manner as for subjects without missing FVC after trial drug discontinuation.

The number of imputations will be set to 1000 in order to ensure adequate efficiency for the estimation of missing data. For each imputed dataset, the same statistical model as defined for

	Plus-Project Statistical Analysis Plan	
	Protocol Number: GALACTIC-1	Version: 1

the primary analysis will be used for the analysis. See Section 7.2.1 for a description of the primary analysis model. The results will be pooled following the standard multiple imputation procedure. See Section 11.4 for further information on the implementation of the multiple imputation approach.

If the primary analysis and sensitivity analysis reach differing conclusions a tipping point analysis will be done. The tipping point analysis will be performed by applying an incremental shift from the imputed FVC value generated under MAR assumption toward the imputed FVC value generated under the MNAR assumption. The value of the shift that overturns the primary analysis result will represent the tipping point.

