14.4.1 Analysis of Primary Efficacy Endpoint

The primary endpoint is described in Section 9.1. The primary efficacy analysis is a random coefficient regression (random slopes and intercepts) model. Treatment and baseline FVC (mL) will be included as a covariate in the analysis model. Other covariates such as age, and gender will be included as covariates unless their inclusion violates model assumptions or impacts stability. Baseline FVC is defined as the FVC result recorded at Visit w0/baseline, unless missing in which case the latest FVC before randomization in the subject's chart result will be used.

The decrease in FVC is assumed to be linear within each subject over 52 weeks. The intercepts and slopes will be assumed to be normally distributed with arbitrary covariance matrix. The within-subject error will be assumed to be independent and normally distributed with mean zero and a common variance. The Kenward-Roger approximation will be used to estimate denominators degrees of freedom.

Section 14.8 details of the approaches to handling of missing data are given.

Significance tests will be based on least-squares means; p-values and two-sided 90% confidence intervals for the difference between the treatment groups will be presented. An intent-to-treat principle will be used. Analyses will be implemented using SAS® Version 9.4 or higher. The assumptions for the primary analysis of decline in FVC will be tested; details will be provided in the SAP. The primary analysis will be based on observed data (but including retrieved drop out

measurements) and will assume remaining missing data are missing at random. The effect of missing data will be investigated using multiple imputation methods which assume that subjects who discontinue treatment will no longer benefit from it in the future. See Section 14.8 for further details of these sensitivity analyses.

Subgroup analyses will be fully specified in the SAP and will include:

- Age
- Gender
- Race
- Ethnicity
- Previous treatment with pirfenidone and/or nintedanib
- Recruitment cohort (e.g., pre- or post- DSMB cutoff, and pre- or post-Protocol version 6.1_UK)

A cumulative distribution plot will be provided, showing the percentage of subjects by change from baseline in FVC in mL at week 52.

Data will be summarized graphically and using summary statistics.

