#### 7.2.2.4 Primary Estimand Sensitivity Analysis

A Mixed Model with Repeated Measures (MMRM) will be fitted to the change from baseline in FVC across all visits with data imputed at Week 52 per the primary estimand (i.e. Week 52 will be attributed the lowest value recorded in the trial when a patient dies). Treatment, visit, baseline FVC, and treatment-by-visit interaction will be fitted as fixed effects. A restricted maximum likelihood (REML) approach will be used, and an unstructured covariance structure shared across treatment groups will be used to model the within-subject errors. If the model fails to converge, a heterogeneous Toeplitz structure (TYPE=TOEPH option in PROC MIXED rather than TYPE=UN) will be used. The Kenward-Roger's correction to degrees of freedom will be applied.

If there are concerns regarding the amount of missing data for the primary estimand, a sensitivity analysis to test the robustness of the MAR assumption used in the main estimand analysis will be performed to assess the results with missing Week 52 FVC data. A multiple imputation approach will be used. Full details of the methods to be followed are given in Section 11.4 and 11.5.

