### 11.3 Primary Estimand Sensitivity and Tipping Point Analyses

A sensitivity analysis to test the robustness of the MAR assumption used in the main estimand analysis will be performed to assess the results with missing Week 52 FVC data.

Non-monotone missing data or missing data at other visits before week 52 will not be imputed. Multiple imputation will be used to handle missing data at week 52. The imputation model will be similar to the statistical model of the primary analysis.

For the imputation of week 52 data that is not available for reasons other than the occurrence of an ICE, the imputation model will be run on the subset of patients who prematurely discontinued trial drug but have been followed up for FVC measurements at week 52. FVC measurements that remain unobserved due to ICEs will still be handled as described in Section 7.2.1. Table 5 below contrasts the MAR approach used in the main estimand analysis with the MNAR approach used in the sensitivity analysis.

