##### Step 1: Run Primary Analysis Model on Observed Data

Run the primary analysis model to get the slope estimates with standard errors (SE) for each treatment group. Let  $\hat{\beta}_T$  and  $\hat{\sigma}_T$  denote the slope and SE estimates in treatment group GB0139 3mg and  $\hat{\beta}_P$  and  $\hat{\sigma}_P$  the slope and SE estimates for placebo.

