##### Step 2: Draw 1000 mean imputation slopes for each treatment

Let  $\beta_T$  and  $\beta_P$  represent the true slopes in drug and placebo respectively with  $f(\beta_T) \sim N(\hat{\beta}_T, \hat{\sigma}_T^2)$  and with  $f(\beta_P) \sim N(\hat{\beta}_P, \hat{\sigma}_P^2)$ , using the slope (SE) estimates obtained in step 1. Draw 1000 random slopes from the appropriate distribution (see Section 11.3) for each treatment.

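### The SAP's missing-data check on FVC drops the protocol's no-further-benefit assumption, and SAP 11.3 and 11.4 disagree on which slopes to impute from

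*SAP*

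**What the plan says.** Protocol 14.4.1 bases the primary analysis on observed FVC, including measurements taken after drug is stopped, and treats what is still missing as missing at random. It then commits to checking this with "multiple imputation methods which assume that subjects who discontinue treatment will no longer benefit from it in the future". It refers to 14.8 for details, but 14.8 covers intercurrent events and gives no imputation rule.

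SAP 7.2.2.4 makes the check conditional: "If there are concerns regarding the amount of missing data for the primary estimand". SAP 11.3 sets the source of the imputation slopes for Week 52: "the imputation model will be run on the subset of patients who prematurely discontinued trial drug but have been followed up for FVC measurements". Its Table 5 gives the assumption as "Subjects with a missing result would have behaved similarly to discontinued subjects with a result who are in the same treatment group". The text below the table spells out the implication: "the treatment effect would have persisted in the same manner as for subjects without missing FVC after trial drug discontinuation".

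SAP 11.4 gives the steps. Step 1 reads "Run the primary analysis model to get the slope estimates with standard errors (SE) for each treatment group", with a heading that refers to observed data and no restriction to discontinued subjects. Step 2 draws the imputation slopes "using the slope (SE) estimates obtained in step 1", while also pointing to 11.3 for the appropriate distribution. Step 4 projects from the last available FVC to Week 52.

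SAP Section 9 lists several changes from the protocol. This is not among them.

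**The concern.** There are two separate problems. First, the protocol fixes an assumption for subjects who stop drug (no further benefit), and the SAP replaces it with one under which a treatment effect may continue, without declaring the change. Second, the SAP gives two sources for the imputation slopes. 11.3 uses discontinued subjects followed to Week 52; 11.4 Step 1 uses everyone. Two programmers could each follow the SAP and obtain different results.

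For the primary endpoint, this is the planned check that departs from missing at random for living subjects without a Week 52 FVC. The repeated-measures model in 7.2.2.4 also assumes missing at random. The supplementary analyses in 7.2.2.3 change which measurements are included or the value given at death. The tipping point in 11.3 runs only if the primary and sensitivity conclusions differ, and it moves only between those two sets of imputed values. If the two sets nearly coincide, it has almost no range. A positive result could then be reported as robust without ever having been tested against loss of benefit after stopping.

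**Working it through.** **Plan's own figure.** Inputs from Protocol 14.6 and the synopsis: difference 100 mL, SD 240 mL, two-sided 10% level, 141 subjects at 2:1 (94 on 3 mg, 47 on placebo), placebo decline 200 mL per year. SE = 240 × √(1/94 + 1/47) = 42.9 mL. 100/42.9 = 2.333, and 2.333 − 1.645 = 0.688, giving power of 75.4%. The stated 75% reproduces.

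**Assumptions.** True on-drug slopes are −100 mL/yr (3 mg) and −200 mL/yr (placebo). A share p of the 3 mg arm has its last FVC at time u (in years), when drug is also stopped. Only Week 52 is imputed, as in Step 4. The documents give neither p nor u, so I use p = 10, 20 and 30% and u = week 12, 26 or 40.

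**Simple form.** If benefit ends at u, the Week 52 difference is 100 × [1 − p(1 − u)]. At week 26 (u = 0.5) the loss is 100 × p × 0.5 = 5, 10 or 15 mL.

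**Slope kept under 11.3.** Suppose discontinued subjects with a Week 52 FVC follow −100 mL/yr until u and −200 mL/yr afterwards. One straight line through weeks 4, 8, 12, 26, 40 and 52 mixes the two periods. The share of the drug effect kept is 1 − Σ(t − t̄)(t − u)₊ / Σ(t − t̄)², where ₊ sets negative values to zero. In weeks, t̄ = 142/6 = 23.67 and Σ(t − t̄)² = 1843.3. For u = 26 the numerator is 16.33 × 14 + 28.33 × 26 = 965.3. The share kept is 1 − 0.524 = 0.48, a slope of −152.4 mL/yr. The same sum gives 0.12 for a stop at week 12 and 0.82 at week 40. So even complete loss of benefit is only partly carried into the imputation.

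**Expected slope difference.** This uses a random intercept and slope model with assumed SDs of 80 (intercept), 200 (slope) and 100 (residual), and last FVC at week 26, in mL over 52 weeks:

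| 3 mg arm missing | 11.4 read literally | 11.3 subset | No further benefit |
|---|---|---|---|
| 10% | 100 | 97.3 | 94.9 |
| 20% | 100 | 94.6 | 89.7 |
| 30% | 100 | 91.8 | 84.4 |

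At 20%, 11.3 shows 5.4 of the 10.3 mL shift, about half. Two other sets of variance components gave 94.8 and 94.4 (11.3) and 90.0 and 89.4 (no benefit). With last FVC at week 12, no benefit gives 91.6, 83.1 and 74.5, and 11.3 gives 92.6, 85.1 and 77.5. At week 40, no benefit gives 98.2, 96.3 and 94.5, and 11.3 gives 99.7, 99.3 and 99.0. The 11.4 column stays at 100 throughout. At the week 26 no-benefit differences, the planning power formula gives 71.5, 67.2 and 62.7%.

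**Size of the 11.3 subset.** If 20% stop and half of those have Week 52 FVC: 94 × 0.2 × 0.5 = 9.4 on 3 mg and 47 × 0.2 × 0.5 = 4.7 on placebo. At SD 240 the slope SEs are 240/√9.4 = 78 and 240/√4.7 = 111 mL/yr. The 94:47 split is itself an assumption, because subjects carried over from the original design were randomised equally to 3 mg and placebo.

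**The case against.** The best defence is that 11.3 is a retrieved-dropout imputation. Its comparison group is discontinued subjects who were measured. If they show little residual benefit, so will the imputed subjects, and the data decide. That suits a treatment-policy estimand, since subjects off study drug may resume usual IPF care (Protocol 10.5), which a whole-arm placebo slope may not reflect. SAP 11.4 calls its steps guidance and refers back to 11.3, as does Step 2, so Step 1 can be read as loose drafting. Protocol 14.4.1 does not name the placebo slope as the way to express no further benefit. The shift of 5 to 15 mL is about 0.12 to 0.35 of the 42.9 mL standard error.

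Much of this stands. A reader might infer that the SAP assumes full benefit continues, the exact reverse of the protocol. That does not follow: the sentence ties persistence to what measured discontinued subjects show. A reader might also infer that the check would always show about no change. That holds only for 11.4 read alone. Nor is this the plan's only departure from missing at random: SAP 7.2.3.1 counts subjects lost to follow-up as having declined by more than 10% for the responder endpoint.

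Two things do not go away. The cross-references do not cancel Step 1's unrestricted wording. And under 11.3 too, the protocol's assumption is never imposed.

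**Conclusion.** The concern holds in this form: the protocol's no-further-benefit analysis is absent from the SAP, its replacement is not declared, and 11.3 and 11.4 conflict on the source of the slopes. Read literally, 11.4 reproduces missing at random on average and leaves the tipping point almost no range. Under 11.3 the check is partial, uses slopes that mix on-drug and off-drug visits, and may rest on very few subjects.

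The sizes are illustrations that depend on assumed dropout and timing. It would be wrong to infer that the primary analysis or the stated power is affected, or that retrieved-dropout imputation is itself unsound. One further limit: the SAP cites protocol version 7.0, while the protocol text supplied describes its changes as version 6.1_UK. The features that Section 9 reports changing do appear in the supplied text, but identical wording of 14.4.1 in version 7.0 cannot be confirmed.

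**What to change.** Before database lock:

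1. In SAP 11.4 Step 1, state that slopes for the retrieved-dropout analysis come from the 11.3 subset, not from the full primary model.
2. Add the protocol's no-further-benefit analysis. For 3 mg subjects with missing Week 52 FVC after stopping drug, draw the later slope from the placebo distribution and apply it from the last available FVC. Placebo subjects also draw from placebo. Keep the 11.3 version as a labelled analysis beside it.
3. Run the tipping point for 3 mg imputations from the own-arm slope to the placebo slope and beyond.
4. Say which discontinued subjects are imputed. 11.3 leaves out data missing because of an intercurrent event, yet SAP 7.2.1 counts treatment discontinuation as one. Record any remaining departure from Protocol 14.4.1 in Section 9.

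The cost is SAP wording, one changed input to the imputation code and one more sensitivity analysis, which will be somewhat less favourable to 3 mg.

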#### **11.4 Multiple Imputation Procedure**

The following steps provide guidance on how missing FVC data at week 52 will be implemented using multiple imputation to allow sensitivity analyses of the primary endpoint. Refer to Section 11.3 for the description of the sensitivity analyses regarding handling of missing data.

##### Step 1: Run Primary Analysis Model on Observed Data

Run the primary analysis model to get the slope estimates with standard errors (SE) for each treatment group. Let  $\hat{\beta}_T$  and  $\hat{\sigma}_T$  denote the slope and SE estimates in treatment group GB0139 3mg and  $\hat{\beta}_P$  and  $\hat{\sigma}_P$  the slope and SE estimates for placebo.

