14.1 Statistical and Analytical Plans

A blinded data review will be conducted prior to database lock. This review will assess the accuracy and completeness of the study database, subject evaluability, and appropriateness of the planned statistical methods.

A statistical analysis plan (SAP) will be prepared and finalized prior to database lock. This document will provide further details regarding the definition of analysis variables and analysis methodology to address all study objectives.

For descriptive statistics categorical data will be presented as frequencies and percentages. Percentages will be based on the number of subjects with non-missing values for the corresponding categorical variable. Continuous data will be presented as number of subjects with non-missing values, mean standard deviation, median, minimum and maximum, as well as the 25th and 75th percentile.

All statistical tests as well as the confidence intervals will be two-sided. The study-wise type I error probability for the confirmatory analyses is set to 10%. 90% confidence intervals are to be calculated, if feasible.

Covariates for the primary analyses will be pre-specified. For secondary analyses these are anticipated to be broadly similar to primary analysis but will be fully specified in the Statistical Analysis Plan (SAP).

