### 7.2.2 Main Estimand and Analysis

The primary analysis will test for superiority of GB0139 3mg compared to Placebo (Plc) for the annual rate of decline in FVC in mL over 52 weeks in subjects not receiving pirfenidone or nintedanib at baseline in the mITT Set. The main estimand for the primary efficacy endpoint is as follows:

- Population: Primary Population, mITT set.
- Variable of interest: Change from baseline in FVC in mL over 52 weeks
- Intercurrent events:
  - Death: FVC attributed the lowest value recorded in the trial when a patient dies

	Plus-Project Statistical Analysis Plan	
	Protocol Number: GALACTIC-1	Version: 1

- Treatment Discontinuation: Analysis will include any FVC measurements after randomised treatment discontinuation
- Initiation of additional IPF therapy (nintedanib or pirfenidone): Analysis will include any FVC measurements after initiation of additional IPF therapy
- Summary measure: Comparison of slopes assessed through the treatment by time interaction.

The null hypothesis is:

$H_0$ : There is no difference in the annual rate of decline in FVC in mL between GB0139 3mg and Plc

The alternative hypothesis is:

$H_a$  : There is a difference in the annual rate of decline in FVC in mL between GB0139 3mg and Plc

A restricted maximum likelihood (REML) approach will be used, with a random coefficient regression (random slopes and intercepts) model fitted to test the hypotheses. The decrease in FVC is assumed to be linear within each subject over 52 weeks [5].

Baseline FVC and time will be fitted as continuous covariates. The treatment group and the interaction term for time by treatment group will be added as fixed effects. Random subject intercept and time effects will be fitted and will be assumed to be normally distributed with arbitrary covariance matrix. The within-subject errors will be assumed to be independent and normally distributed with mean zero and a common variance. The Kenward-Roger approximation will be used to estimate denominators degrees of freedom.

The statistical model will be as follows:

$$Y_{itk} = (\alpha + a_i + \tau_k) + \beta_f FVCb_i + (\gamma + \beta_3 T_3 + g_i) t + \varepsilon_{it}$$

where:

$Y_{itk}$  is the change from baseline measured for ith patient at time t (actual time) in treatment group k

$t$  is the time since randomization in years

$T_3 = 1$  if the subject is in the GB0139 3mg group, otherwise  $T_3 = 0$

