##### Step 3: Draw 1000 slopes for each subject

From the respective SE for each treatment slope from step 1, derive an approximation for the SD as  $SE \cdot \sqrt{n}$  where  $n$  is the number of subjects in the model randomized to the relevant treatment. For each mean imputation slope obtained in step 2, draw an individual slope for each subject randomized to the respective treatment from a normal distribution with mean equal to the mean imputation slope and relevant SD as derived above.

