##### Step 4: Impute any monotonic missing FVC data at 52 weeks using each slope

- a) Considering that the withdrawal of a subject leading to missing data can occur at any time during the study, the timepoint of the last available FVC value has to be taken into account to impute the missing FVC value at 52 weeks:
- b)  $FVC_{week\ 52\ imputed_{ij}} = \text{last FVC value available}_i + \hat{\beta}_{ij} * (\text{time between date of last FVC value available } i \text{ and planned 52 week timepoint [days]})$

	Plus-Project Statistical Analysis Plan	
	Protocol Number: GALACTIC-1	Version: 1

where  $i$  denotes the indicator of the  $i$ th subject,  $j$  the indicator of the  $j$ th imputation and  $\beta_{ij}^{\wedge}$  denotes a random slope sampled from the distribution mentioned above for the  $i$ -th subject in the  $j$ -th imputation.

- c) Create 1000 imputed FVC datasets for subjects with monotonic missing FVC data at 52 weeks including replicates of any FVC data collected in the study with the addition of the imputation specific 52 week result.
- d) Create 1000 identical FVC datasets for subjects with no monotonic missing FVC data at 52 weeks.
- e) Combine data from b and c.

Step 5: Run primary analysis model on each imputed dataset

Run the model of the primary analysis on each imputed dataset, using a "by \_IMPUTATION\_" statement to obtain 1000 parameter estimates (variable = estimate) and standard errors (variable = stderr).

Step 6: Combine the results obtained in step 4 using PROC MIANALYZE

```
Ods output ParameterEstimates=step5;
Proc Mianalyze data=step5 ;
modeffects estimate;
stderr stderr;
Run;
```

	Plus-Project Statistical Analysis Plan	
	Protocol Number: GALACTIC-1	Version: 1

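### SAP 11.4 Step 1 takes the imputation slopes and spread from the unrestricted primary model, death scores included, and so conflicts with the donor subjects named in SAP 11.3 and Table 5

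*SAP*

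**What the plan says.** The primary estimand uses a composite strategy for death: "FVC attributed the lowest value recorded in the trial when a patient dies" (SAP 7.2.2). SAP 7.2.1 lists death as an intercurrent event (ICE), with treatment discontinuation and starting pirfenidone or nintedanib.

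The source of the imputation slopes is described in three ways:

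- **SAP 11.4, Steps 1–3.** Step 1: "Run the primary analysis model to get the slope estimates with standard errors (SE) for each treatment group". Step 2 draws mean slopes from those estimates. Step 3 takes the same SE to "derive an approximation for the SD as" SE × √n. No subset is named and no record is excluded. The Step 1 heading does refer to observed data, and Step 2 points back to 11.3.
- **SAP 11.3, text.** For Week 52 data missing for reasons other than an ICE, the imputation model is run on subjects who stopped trial drug early but were followed for FVC at Week 52. It adds: "FVC measurements that remain unobserved due to ICEs will still be handled as described in Section 7.2.1".
- **SAP 11.3, Table 5.** The subjects to be imputed fall under "No FVC result but alive at Week 52". The donors are subjects with an ICE whose FVC is not missing, while the assumption column speaks of discontinued subjects.

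Step 4 is then worded broadly: "Impute any monotonic missing FVC data at 52 weeks using each slope". SAP 7.2.2.4 sends the reader to 11.4 and 11.5, not 11.3, for the method. The code in 11.5 is the primary model without a subset.

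**The concern.** Table 5 presents this analysis as the missing-not-at-random check: living subjects without a Week 52 value are assumed to behave like discontinuers who have one. Slopes from the full primary fit cannot express that. They are the arm slopes on which the missing-at-random analysis already relies, so the check would largely repeat the assumption it is meant to test.

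The death scores add a second problem. They are attributed values, often more than a litre below baseline. A few of them steepen the arm slopes and inflate the SE. Step 3 turns that SE into a subject-level SD, and Step 4 uses both to generate FVC for people known to be alive. Deaths already counted once through the composite score then also shape the values given to survivors.

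This is the only planned departure from missing at random for living subjects on the primary endpoint, and disagreement with the primary analysis triggers the tipping-point analysis. If the donor set is chosen after unblinding, that choice is made with the results in view.

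**Working it through.** **1. The plan's own figure.** The documents give no figure for the imputation, so the sample size is the anchor. Protocol 14.1: "The study-wise type I error probability for the confirmatory analyses is set to 10"% and "All statistical tests as well as the confidence intervals will be two-sided". SAP 3.1: difference 100 mL, SD 240 mL, N = 141 at 2:1, taken as 94 and 47.

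SE = 240 × √(1/94 + 1/47) = 42.9 mL. 100/42.9 = 2.33. Power = Φ(2.33 − 1.645) = 75.4%, against 75% stated. The original design also reproduces: 150 per arm, SD 280 and two-sided 5% give 87.1%, against about 87%.

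**2. Step 1 fitted with and without death scores.** Simulated trials of 94:47, random intercept and slope, true slopes −100 (3 mg) and −200 (placebo) mL/yr, 15% dropout, death score placed at Week 52. Setting A: baseline 2700 (SD 650) mL, slope SD 200, residual SD 90, lowest FVC 1000 mL, 25 trials per row. Setting B: baseline 2800 (SD 750) mL, slope SD 220, lowest FVC taken from the simulated data, 12 trials per row. All of these are assumptions except the 200 mL placebo decline and the 100 mL difference.

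| Setting | Deaths | Slopes, 3 mg / placebo (mL/yr) | Step 3 SD (mL/yr) |
|---|---|---|---|
| A | none | −106 / −197 | 238 |
| A | 7 (5%) | −197 / −271 | 484 |
| A | 14 (10%) | −282 / −375 | about 600 |
| B | death scores left out | −95 to −99 / −183 to −209 | about 250–265 |
| B | 2% | −131 / −241 | about 375 |
| B | 5% | −195 / −288 | about 570 |
| B, baseline 2300 | 5% | −180 / −271 | about 505 |
| B | 10% | −304 / −419 | about 750 |

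Some fits in setting A gave convergence warnings, so here is a hand check that needs no model fit. In setting A a death score is a change of 1000 − 2700 = −1700 mL. The allocation-weighted mean slope is −(94 × 100 + 47 × 200)/141 = −133. With 5% deaths the mean shifts by 0.05 × (−1700 + 133) = −78 mL/yr, and the SD becomes √(238² + 0.05 × 0.95 × 1567²) = 416, or 1.7 times 238. The 5% rows above give ratios of 1.9 to 2.2.

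**3. One imputed living placebo subject (setting A, none versus 7 deaths).**

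- Last seen at Week 12: mean change 40/52 × −197 = −152 against 40/52 × −271 = −208 mL; SD 183 against 372 mL.
- Last seen at Week 40: 12/52 × −197 = −45 against 12/52 × −271 = −63 mL; SD 55 against 112 mL.

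**4. Carried through to the pooled result.**

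- Deaths random across arms, setting A, about 108 trials, 8 imputations. With 7 deaths: primary difference 110 (SE 86) mL/yr; imputation with death scores in Step 1, 109 (SE 87); without them, 109 (SE 81). SE ratio 87/81 = 1.07. With 14 deaths: 97 (114), 96 (116) and 98 (106); ratio 116/106 = 1.09. Agreement with the primary conclusion at 10% was 94% with death scores and 94% without (7 deaths), and 94% and 97% (14 deaths).
- A second run with 7 deaths, 15–25% dropout and 40 trials per setting gave a Step 3 SD rising from about 250 to 480. With deaths split 2:1, the difference moved by 4 mL/yr or less and the SE rose about 7–13%. With 5 placebo and 2 active deaths, the difference moved by about 12–20 mL/yr.

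**5. Why imbalance matters.** With 5/47 placebo deaths the placebo slope shifts by 0.106 × (−1700 + 200) = −160 mL/yr. With 2/94 active deaths the active slope shifts by 0.021 × (−1700 + 100) = −34. The gap between imputation slopes widens by about 126 mL/yr, in favour of the arm with fewer deaths. If 15–25% of subjects were imputed over a full missing year, that would be 126 × 0.15 = 19 to 126 × 0.25 = 32 mL. Most miss only part of the year, so 12–20 is plausible. With a 2:1 split both slopes shift by about −75 to −80 and the gap hardly changes.

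**The case against.** The intended procedure can be reconstructed. The introduction to 11.4 calls its steps guidance and refers to 11.3 for the handling of missing data. The Step 1 heading mentions observed data, and a death score is attributed, not observed. Step 2 points to 11.3, whose donor subset cannot contain anyone who died. All of this stands, and it rules out one stronger reading: that living subjects will certainly be imputed partly as if they had died. It does not settle the matter. The heading may only contrast Step 1 with the imputed datasets of Step 5, the instruction beneath it names no subset, and 7.2.2.4 sends the programmer to 11.4. Table 5's donor rule differs from the 11.3 text in any case, since it also takes in subjects who started IPF therapy and leaves open whether a death with an attributed value counts.

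A reader might also infer that no reading works, because dropping death scores from Step 1 would leave deceased subjects to be imputed as survivors under Step 4's wording. The documents do not support this. Section 11.3 limits imputation to data missing for reasons other than an ICE and keeps the death handling, and Table 5 is confined to living subjects.

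Step 4e, which combines items b and c, might be read as discarding subjects with an observed Week 52 value. Item b is a formula, and item d has no purpose unless it is combined, so this is a lettering slip.

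Finally, 5% should not be read as an expected death rate. In Protocol 14.4.2.1 it is a threshold below which time to death would not be analysed, and SAP section 9 removes it.

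**Conclusion.** The point holds as a specification conflict with a material consequence under the literal reading. Step 1, the 11.3 text and Table 5 give three different sources for the imputation slopes. Following Step 1 as written puts death scores into the slopes and spread for living subjects and does not test the assumption that Table 5 states.

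At an assumed 5% of deaths, the subject-level SD roughly doubles and both arm slopes steepen by about 75–105 mL/yr. The effect on the pooled result is smaller: an SE about 7–13% larger, little movement in the difference when deaths follow allocation, and about 10–20 mL/yr when they are imbalanced as in the 5-versus-2 case. That is up to a fifth of the 100 mL planning difference. A claim that the check would generally fail because of deaths goes too far: with deaths random across arms, agreement with the primary conclusion was 94% or higher either way.

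The documents give no death rate, baseline FVC or lowest FVC, and the simulations are small, so only direction and rough size should be relied on. They compare fits with and without death scores; the number of discontinuers who will be followed to Week 52 is not stated, so no figure is put on using that subset. The primary result is unaffected. The check is a sensitivity analysis, conditional in 7.2.2.4 although 11.3 says it will be done. It should be corrected, but it does not threaten the main analysis.

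**What to change.** Amend SAP 11.3 and 11.4 before unblinding:

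- **Step 1:** fit the model for the imputation slopes and SEs on real, non-attributed FVC values of the 11.3 reference subset (trial-drug discontinuers followed for FVC at Week 52).
- **Table 5:** reword the donor description to name the same subset.
- **Step 4:** state that only subjects alive at Week 52 without an FVC result are imputed, as 11.3 and Table 5 already intend.
- **Step 5:** state that deceased subjects keep their attributed death score in every dataset analysed.
- **Step 4e:** combine c and d.

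The cost is a few sentences and a filter in the program, with no new data. The downside is that the 11.3 subset may be small, so its slopes will be less precise than those of the full fit.
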